7.1.5 Post-Treatment Follow-up

7.1.5.1 Safety Follow-up Visit

All subjects will have a subsequent visit scheduled 10 weeks (± 2 weeks) after the last administration of MSB0011359C. The visit will include the following full assessment of safety parameters (refer to Table 1, Table 2, and Table 3):

- For subjects in the GC, ESCC, and BTC expansion cohorts only, patient-reported outcome questionnaires (PGIS, EORTC QLQ-C30, EORTC QLQ-BIL21, EORTC QLQ-HCC18, EORTC QLQ-OES18, and EORTC QLQ-STO22) will be completed prior to any study-related procedures as indicated in Table 2.
- AEs that are deemed attributable to trial drug by the Investigator and concomitant medications (including further anticancer therapy) will be documented.
- Vital signs and body weight will be measured.

CONFIDENTIAL INFORMATION

- Physical examination will be performed.
- Dermatological assessment.
- SpO₂ will be measured.
- ECOG PS will be assessed.
- 12-lead ECG will be assessed.
- Laboratory testing consisting of the following will be assessed:
 - o Hematology, hemostaseology, full serum chemistry, and full urinalysis
 - o Free T4, and TSH levels.
 - PK sample will be collected.
 - ADA sample. The term for ADA on the CRF is human antihuman antibodies (HAHA)
 - Samples for viral load testing (HBV, HCV; HCC cohort only).
- A urine β-HCG pregnancy test (in women of child bearing potential) will be conducted.

7.1.5.2 Long-term Follow-up/Trial Termination

All SAEs ongoing at the End-of-Treatment visit must be monitored and followed up by the Investigator until stabilization or until the outcome is known, unless the subject is documented as "lost to follow-up" or started a new anticancer therapy. In addition, all trial drug-related SAEs occurring after End-of-Treatment visit and ongoing at the Safety Follow-up visit have to be followed up in the same manner.

Subjects without PD at the End-of-Treatment visit will be followed up for disease progression (CT/MRI scans every 12 weeks) until PD.

After the End-of-Treatment visit, subjects will be followed quarterly (± 14 days) for survival (including assessment of any further tumor therapy). The survival follow-up will continue until 1 year after the last subject receives the last dose of MSB0011359C.

After completion of the Follow-up period or at discontinuation of the trial, whatever is applicable / comes first, the appropriate eCRF section for Trial Termination must be completed.

7.1.6 Blood Consumption for Clinical Assessments

The overall amount of blood to be drawn from a single subject must not exceed 60 mL/day and 300 mL in an 8-week period for safety laboratory testing, pregnancy testing, PK analyses, and antibody evaluation.

CONFIDENTIAL INFORMATION

7.2 Demographic and Other Baseline Characteristics

The assessments and procedures described in this section must be performed during the Screening period.

7.2.1 Demographic Data

The following demographic data will be recoded:

- Subject identifier
- Date of birth
- Sex
- Ethnicity
- Race.

7.2.2 Diagnosis of Tumor

The tumor disease information that will be documented and verified at the Screening visit for each subject includes:

- Detailed history of the tumor, including histopathological diagnosis, grading and staging in accordance with the Union Internationale Contre le Cancer Tumor Node Metastasis Classification at diagnosis.
- All therapy used for prior treatment of the tumor (including surgery, radiotherapy and chemotherapy, immunotherapy, etc).
- Any other conditions that were treated with chemotherapy, radiation therapy, or immunotherapy.
- Current cancer signs and symptoms and side effects from current and/or previous anticancer treatments.
- Current cancer disease status.

7.2.3 Medical History

In order to determine the subject's eligibility to the trial, a complete medical history of each subject will be collected and documented during Screening, which will include, but may not be limited to, the following:

- Past and concomitant non-malignant diseases and treatments.
- All medications taken and procedures carried out within 30 days prior to Screening.

CONFIDENTIAL INFORMATION

For the trial entry, all the subjects must fulfill all inclusion criteria described in Section 5.3.1, and none of the subjects should have any exclusion criterion from the list described in Section 5.3.2.

7.2.4 Vital Signs and Physical Examination

Vital signs including body temperature, respiratory rate, heart rate (after 5-minute rest), and arterial blood pressure (after 5-minute rest), body weight and height will be recorded at study entry.

A complete physical examination will be performed. Oxygen saturation will be measured. An ophthalmology examination including slit lamp evaluation inclusive of the anterior segment and with visual acuity should be conducted.

The ECOG PS will be documented during the Screening period.

7.2.5 Computed Tomography or Magnetic Resonance Imaging Scans for Tumor Assessment at Baseline

A CT scan or MRI (if MRI is used, CT of chest is mandatory) of the chest, abdomen, and pelvis (at a minimum and other established assessments of tumor burden if CT/MRI imaging is not sufficient for the individual subject; other regions as specifically required for specific tumor indications) will be performed within 28 days prior to trial treatment start in order to document the baseline status of the tumor disease using RECIST 1.1 target and nontarget lesions and secondarily using mRECIST for subjects in the HCC cohort (see vendor manual). However, if the results of a CT scan or MRI performed within 4 weeks prior to first treatment are available, the Screening CT/MRI does not need to be performed.

A brain CT/MRI scan (either, contrast preferred) is required at Screening if not performed within the previous 6 weeks. Thereafter, brain CT/MRI scan should be done if clinically indicated by development of new specific symptoms.

A bone scan should be done at Screening as clinically indicated.

7.2.6 Cardiac Assessments

A 12-lead ECG will be recorded at Screening. The ECG will be recorded under institution's guidance after the subject has been in a supine position breathing quietly for 5 minutes. The ECG results will be used to evaluate the heart rate, atrial-ventricular conduction, QR, QT, RR duration and corrected QT intervals, and possible arrhythmias.

The ECGs will be documented by recording date and time of collection. All ECG results must be reviewed at the site by the Investigator or a medically qualified designee for clinical management of the subject.

CONFIDENTIAL INFORMATION

The Investigator will judge the overall interpretation as normal or abnormal. If abnormal, it will be decided if the abnormality is clinically significant or not clinically significant and the reason for the abnormality will be recorded on the eCRF. Abnormal values will not be recorded as AEs unless they are the reason for discontinuation of the trial IMP due to AEs or are SAEs.

7.2.7 Clinical Laboratory Tests

Blood samples will be collected at Screening for clinical laboratory parameter evaluations. These clinical laboratory test results will serve not only as the baseline values for subsequent safety clinical laboratory evaluations during the trial, but also help to make sure that each enrolled subject fulfills all the trial entry criteria as listed in Section 5.3.1 and does not meet any of the trial exclusion criteria for laboratory parameters as listed in Section 5.3.2. Detailed description of laboratory assessments is provided in Section 7.4.3.

7.3 Efficacy Assessments

For all subjects in all cohorts, tumor response assessment will be performed by CT scan or MRI (if MRI is used, CT of chest is mandatory; for subjects in the HCC cohort, contrast is mandatory) imaging of the chest/abdomen/pelvis (plus other regions as specifically required for specific tumor types) and other established assessments of tumor burden if CT/MRI imaging is insufficient for the individual subject. All the scans performed at Baseline and other imaging performed as clinically required (other supportive imaging) need to be repeated at subsequent visits. In general, lesions detected at Baseline need to be followed using the same imaging methodology and preferably the same imaging equipment at subsequent tumor evaluation visits.

A brain CT/MRI scan (either, with contrast preferred) is required at Screening if not performed within the previous 6 weeks. Thereafter brain CT/MRI scan should be performed, if clinically indicated by development of new specific symptoms. A bone scan should be performed at Screening and beyond as clinically indicated. Skin metastasis can be used as target lesions according to RECIST 1.1 using measurements by caliper, if they fulfill RECIST 1.1 for target lesions as described below. The presence of new cutaneous lesions will be considered diagnostic of progression for RECIST 1.1, even if not imaged. For each subject, the Investigator will designate 1 or more of the following measures of tumor status to follow for determining response: CT or MRI images of primary and/or metastatic tumor masses, physical examination findings, and the results of other assessments. All available images collected during the trial period will be considered. The most appropriate measures to evaluate the tumor status of a subject should be used. The measure(s) to be chosen for sequential evaluation during the trial have to correspond to the measures used to document the progressive tumor status that qualifies the subject for enrollment. The tumor response assessment will be assessed and listed according to the Schedule of Assessments (refer to Table 1 and Table 2).

The foreseen treatment duration is until disease progression verified by a scan subsequent to the initial documentation of PD, unacceptable toxicity, or any criterion for withdrawal from the trial

CONFIDENTIAL INFORMATION

or IMP occurs (see Section 5.5). Before stopping the treatment, PD should be confirmed by imaging 4 to 6 weeks (preferably 6 weeks, but not later) after progression has been diagnosed according to RECIST 1.1. If progression is based on the occurrence of a new lesion in an area not scanned at Baseline, a further on-study scan 6 weeks later should be considered before performing the End-of-Treatment visit. Treatment may be continued despite progression according to RECIST 1.1 at any time if:

- There are no new symptoms or worsening of existing symptoms.
- There is no decrease in ECOG PS.
- The Investigator does not consider it necessary to administer a salvage therapy.

The treatment should be stopped immediately, if the subject does not tolerate MSB0011359C anymore or if therapeutic failure occurs, which requires urgent treatment with an additional drug or results in clinically significant progression/deterioration.

Tumor responses to treatment will be assigned based on the evaluation of the response of target, nontarget, and new lesions according to RECIST 1.1 (all measurements should be recorded in metric notation) and secondarily using mRECIST for subjects in the HCC cohort.

• To assess objective response, the tumor burden at baseline will be estimated and used for comparison with subsequent measurements. At baseline, tumor lesions will be categorized in target and nontarget lesions according to RECIST 1.1 and secondarily using mRECIST for subjects in the HCC cohort.

Results for these evaluations will be recorded with as much specificity as possible so that pre- and post-treatment results will provide the best opportunity for evaluating tumor response.

Any CR or PR should be confirmed according to RECIST 1.1. In the case of a PR or CR, a confirmatory CT or MRI scan must be done no sooner than 4 weeks (preferably at the scheduled 6-week interval).

The Investigator may perform scans in addition to a scheduled trial scan for medical reasons or if the Investigator suspects PD.

As outlined in Section 5.1, treatment should continue with the investigational drug and the subject may remain on study according to the Investigator's decision and in agreement with the subject in case of PD according to RECIST 1.1. Following PD on RECIST 1.1, modified "immune-related response criteria" (irRC; see below and Nishino 2013) should be used as guidance for further clinical care.

Subjects who have experienced a CR, PR or SD should continue treatment through the end of 12 months after confirmation, although additional treatment is possible. If the Investigator believes that a subject may benefit from treatment beyond 12 months, it may be permissible after

CONFIDENTIAL INFORMATION

discussion with the Medical Monitor. Subjects re-initiating treatment should be assessed according to the Schedule of Assessments (Table 1 and Table 2).

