2.2.2 Central Reader and Independent Endpoint Review Committee

A central facility will read and interpret all radiographic scans for subjects enrolled in the expansion cohorts (for dose escalation, radiographic scans will be read locally). The data for all

67 DV

images will be transferred from trial sites to the central reading center for evaluation. Scans will be evaluated at the central facility in accordance with Response Evaluation Criteria in Solid Tumors Version 1.1 (RECIST 1.1, see Eisenhauer 2009) and secondarily using modified RECIST (mRECIST) for subjects in the hepatocellular carcinoma (HCC) cohort. The imaging data will be transferred to the Sponsor or designee at regular intervals. A manual from the vendor will be provided to each trial site. The results of the central read will not be available in real time and will not be used for trial subject management. Local interpretation of radiographic scans will be used by the Investigator for real-time trial subject management decisions.

[figure not shown]
For subjects enrolled in the expansion cohorts, an Independent Endpoint Review Committee (IRC) will perform a blinded determination as to whether the criteria for tumor response or progression according to RECIST 1.1 have been met. The role of the IRC will be to review radiographic image findings and physical findings for the determination of the time point overall response and date of disease progression according to RECIST 1.1 for each subject. The full membership, mandate, and processes of the IRC will be detailed in the IRC charter. The results from the IRC will not be available in real-time and will not be used for trial subject management. The Investigator will determine tumor response or progression according to RECIST 1.1 for real-time trial subject management decisions.

3 Background Information

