A Phase II study of a small molecule kinase inhibitor of TGF signaling, LY2157299, revealed a subgroup of alpha-fetoprotein (AFP) responders in sorafenib failures or sorafenib intolerant HCC patients who had a substantial and significant increase in overall survival (OS) compared with the non-AFP responders, with median OS of 93.1 weeks versus 29.6 weeks, respectively, suggesting possible clinical activity of a TGF inhibitor in HCC (Faivre 2014).

MSB0011359C, is comprised of an extracellular domain of the human TGFβ receptor TGFβRII covalently joined via a glycine/serine linker to the C terminus of each heavy chain of the fully human IgG1 anti-PD-L1 antibody, avelumab. Given the emerging picture for PD-1/PD-L1 class, in which responses are apparent but with room for increase in effect size, it is assumed that co-targeting a complementary immune modulation step will improve tumor response. A similar TGF-targeting agent, fresolimumab, which is a monoclonal antibody targeting TGFβ1, 2 and 3, showed initial evidence of tumor response in a Phase I trial in subjects with melanoma. The objective response was observed in 1 of 28 subjects with 6 subjects showing stable disease (Morris 2014).

A reasonable safety profile is anticipated when targeting these pathways. The safety of the PD-1 / PD-L1 class continues to emerge but appears to be substantially less adverse compared with the cytotoxic T lymphocyte antigen-4 (CTLA-4) class of T cell checkpoint inhibitors (Dolan 2014; Sznol 2015). Two TGFβ inhibiting biologics have been administered in clinical trials and showed an acceptable human safety profile in humans that did not include immune-related events.

> CONFIDENTIAL INFORMATION

Fresolimumab was studied in Phase I trial in subjects with cancer (28 with melanoma, 1 with renal cell carcinoma). No DLTs were observed and 15 mg/kg, the highest dose tested, was determined to be safe (Morris 2014). The major AE was emergent skin tumors and hyperkeratosis. In a small trial of idiopathic pulmonary fibrosis, the most common AE was fatigue (Lonning 2011). In a study of 16 subjects with focal segmental glomerulosclerosis, the only AE was pustular rash in 2 subjects (Trachtman 2011). Transforming growth factor-β1 monoclonal antibody (TβM1), an antibody inhibiting the TGFβII receptor, was well tolerated when studied at doses as high as 240 mg with diarrhea as the only DLT event (Cohn 2014). Notably, one event of low hemoglobin (Hgb) was observed in the high dose group

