3.4.5 Rash with Hyperkeratosis/Keratoacanthoma/Squamous Cell Carcinoma of the Skin

Phase I information from a TGF antibody showed excess acanthomas, some with atypical features, and one confirmed squamous cell carcinoma (Morris 2014). A genetic disorder in the TGF pathway is also known to be associated with skin tumors (Goudie 2011). Based on this information, skin tumors are considered a potential risk. Monitoring will include skin assessments as defined in the Schedules of Assessments (see Table 1 and Table 2). Management should be discussed with the Medical Monitor on a case-by-case basis. Dermatological consults should be requested as needed. Rash with hyperkeratosis/keratoacanthoma/squamous cell carcinoma of the skin are considered as an important identified risk and AESIs requiring expedited reporting from the Investigator to the Sponsor. Any suspicious lesion should be biopsied. For nonserious AESIs, an AESI Report Form has to be completed; for serious events, an SAE Report Form has to be used (see Section 7.4.1.4).

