- Keratoacanthoma and squamous cell carcinoma of the skin. Any suspicious skin lesion should be biopsied and be surgically removed. The Study Medical Monitor should be consulted.
- Grade 3 or 4 dematological irAEs, treatment should be delayed and treatment started according to Table 5, if condition improves to Grade 1, treatment may be resumed. If ≥ 2 consecutive doses are missed, the Medical Monitor should be consulted.
- Grade 3 or 4 symptomatic endocrinopathies (eg, thyroiditis or hypophysitis), treatment should be delayed and treatment started according to Table 5, if condition improves to Grade 1, treatment may be resumed. If ≥ 2 consecutive doses are missed, the Medical Monitor should be consulted
- Other immune-related ADRs, see Table 5.

Any Grade 2 ADR should be managed as follows:

- If a Grade 2 ADR resolves to Grade ≤ 1 by the last day of the current cycle, treatment may continue.
- If a Grade 2 ADR does not resolve to Grade ≤ 1 by the last day of the current cycle but is manageable and/or not clinically relevant, the ADR should be discussed with the medical monitor. Based on the discussion, it is possible that the infusion will be given on the following cycle. If at the end of the following cycle, the event has not resolved to Grade 1,

CONFIDENTIAL INFORMATION

another discussion should occur with Medical Monitor to consider permanently discontinuing treatment with MSB0011359C.

- Upon the second occurrence of the same Grade 2 ADR in the same subject (except for fatigue and hormone insufficiencies that can be managed by replacement therapy), continuation of treatment with MSB0011359C has to be discussed with the medical monitor and may lead to permanently discontinuation.
- Infusion-related reactions and hypersensitivity reactions (Grades 1 to 4) should be handled according to the guidelines provided in Section 6.5.4.1 and Section 6.5.4.2, respectively.
- Anemia should be handled according to the guidelines provided in Section 6.5.4.4.
- If immune-related ADRs, see Table 5.

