14.1 Best Overall Response

Best overall response (BOR) will be assessed based on the tumor response at different evaluation time points from baseline until the first documented disease progression. The unconfirmed BOR will be defined by the best overall response reached by the participant during this period, while the confirmed BOR will have to meet additional rules of confirmation as defined in the following sections. Only tumor assessments performed before the start of any further anticancer treatment will be considered in the assessment of BOR. Clinical deterioration will not be considered as documented disease progression.

Objective Response (OR) is defined as complete response (CR) or partial response (PR) according to evaluation criteria from start date until documented disease progression. Patients who do not have an on-treatment radiographic tumor assessment due to early progression, who receive anti-tumor treatments other than the study treatments prior to reaching a CR or PR, or who die, progress, or drop out for any reason prior to reaching a CR or PR will be counted as non-responders in the assessment of OR. Each patient will have an objective response status (0: no OR; 1: OR). OR rate (ORR) is the proportion of patients with OR in the analysis set.

Disease Control Rate (DCR) is defined as the proportion of participants with BOR according to evaluation criteria of CR, PR, or SD. For RECIST 1.1 as adjudicated by IRC, non-CR/non-PD will also be considered in DCR evaluation.

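### Protocol 7.3 scores any new skin lesion as RECIST 1.1 progression without limiting the rule to metastases of the study tumour, so read literally a drug-related skin lesion would be a false PD

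*Protocol*

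**What the plan says.** The progression rule for skin is in Protocol Section 7.3: "The presence of new cutaneous lesions will be considered diagnostic of progression for RECIST 1.1, even if not imaged". It sets no condition on histology or on attribution to the study tumour. The sentence just before it is about metastases: "Skin metastasis can be used as target lesions according to RECIST 1.1 using measurements by caliper".

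Other sections deal with skin lesions as effects of the drug:

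- Section 3.4.5: "Rash with hyperkeratosis/keratoacanthoma/squamous cell carcinoma of the skin are considered as an important identified risk and AESIs". The same paragraph also calls skin tumours a potential risk.
- Section 3.1, on a related anti-TGFβ antibody: "The major AE was emergent skin tumors and hyperkeratosis".
- Section 7.4.1.1.2 classes squamous cell cancer of the skin as a new, secondary cancer.
- Section 5.1.7.2, in its list of exceptions for Grade 3 drug reactions: "Keratoacanthoma and squamous cell carcinoma of the skin. Any suspicious skin lesion should be biopsied and be surgically removed".
- SAP Section 16.2.3.3 tabulates the same lesions as skin adverse events possibly due to TGF-β inhibition.

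On the endpoints, SAP Section 14.1 states: "Best overall response (BOR) will be assessed based on the tumor response at different evaluation time points from baseline until the first documented disease progression". SAP Sections 14.2 and 14.3 end duration of response and PFS at the first date of PD or a qualifying death. On central review, Protocol Section 2.2.2 states: "The role of the IRC will be to review radiographic image findings and physical findings for the determination of the time point overall response".

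**The concern.** The rule covers every new cutaneous lesion, while the protocol itself anticipates new cutaneous lesions that are not the study tumour. An assessor who applies Section 7.3 to the letter would record a drug-related keratoacanthoma or a primary skin cancer as progression of a gastric, oesophageal or biliary cancer.

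That error would not be random noise. It would arise from the drug's own mechanism and push in one direction: fewer responses, shorter PFS and shorter duration of response. Central review does not clearly screen it out, because the IRC is told to use physical findings as well as images.

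**Working it through.** The plan gives no figure for this rule, so there is nothing to reproduce. The check is mainly textual, followed by an illustration of size.

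**1. Is there an exclusion elsewhere?** None was found. Sections 3.4.5 and 5.1.7.2 and footnote e of Table 2 call for biopsy of suspicious skin lesions, but no passage feeds the result into the response assessment. The protocol does write such limits for other sites. Section 7.3.2 treats new liver lesions that miss its criteria as equivocal, and Section 6.5.1 separates the need for palliative bone radiotherapy from PD. SAP Section 14.1 excludes only clinical deterioration as progression.

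**2. Can a skin lesion come before a response?** Yes. Table 2 schedules dermatological assessment from Day 15, and the first post-baseline tumour evaluation is at Week 7 (Day 43).

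**3. Which endpoints are exposed?**

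| Endpoint and source | Where it ends | Effect of a false PD |
|---|---|---|
| BOR and ORR, SAP 14.1 to 14.1.2 | First documented PD; confirmed CR or PR needs two determinations at least 4 weeks apart, before progression | Response lost only if the lesion is scored before the response is established |
| Duration of response, SAP 14.2 | First date of PD; no confirmation | Shortened |
| Duration of response, Protocol 8.5.3.1 | PD by IRC that is later confirmed | Narrower; a lesion that was removed may never be confirmed |
| PFS, SAP 14.3 | First date of PD | Shortened |
| PFS, Protocol 8.5.3.1 | Radiological PD by IRC | Narrower; a lesion that was not imaged arguably does not count |

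The exposure is therefore clearest for BOR, for investigator-assessed endpoints and under the SAP definitions. The last four rows also show a mismatch between protocol and SAP.

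**4. How large could it be?** The documents give no rate of such lesions for this drug, so the rate q is assumed to be 3% to 10%. The only anchor is one confirmed squamous cell carcinoma (Section 3.4.5) among 28 + 1 = 29 subjects given the related antibody (Section 3.1): 1/29 = 3.4%. The number of keratoacanthomas is not given.

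- Affected subjects in a cohort of 30: 30 × 0.03 = 0.9 to 30 × 0.10 = 3.0.
- Chance of at least one in 30, 1 − (1 − q)^30: 65% at q = 3.4%, 79% at 5%, 96% at 10%.
- One response lost in 30: 1/30 = 3.3 points. For example, 6/30 = 20.0% (95% Clopper-Pearson CI 7.7 to 38.6) becomes 5/30 = 16.7% (5.6 to 34.7).
- BTC enlargement rule, 5 or more responders of 20, with a true ORR of 25% and response probability 0.25 × (1 − q): 58.5% with no misclassification, 55.0% at q = 3.4%, 48.0% at q = 10%.

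These are upper bounds. The counts assume that every such lesion is scored as PD ahead of true progression, and the BTC figures assume that every lesion comes before the response.

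**The case against.** The strongest reply is context. The preceding sentence is about skin metastases, so the rule may mean only that new cutaneous tumour disease counts without a scan. That is probably the intent, and it stands as a reason to call this a wording defect. It does not remove the defect, because the rule as printed has no such limit.

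A reader might infer more than the documents support:

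- **That IRC endpoints are equally exposed.** Protocol 8.5.3.1 asks for radiological PD for PFS and confirmed PD for duration of response, and IRC processes sit in a charter that is not among the documents. IRC handling is unknown. The looser SAP wording means that the protocol is not a reliable safeguard either.
- **That a false PD would end treatment.** Sections 5.5.1 and 7.3 allow treatment to continue past a first PD under stated conditions and call for PD to be confirmed by imaging before stopping.
- **That the AESI, DLT and drug-reaction text contradicts Section 7.3.** Safety classification and response category are separate. Those sections show that such lesions are foreseen, not that they are scored as PD.
- **That the drug is known to cause skin tumours at a material rate.** Section 3.4.5 uses both potential and identified risk, and the tumour data it cites come from a different antibody.
- **That affected responders would go unseen.** SAP Sections 14.1.1 and 14.1.2 list responses that occur after a first progression.

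The efficacy endpoints are also secondary. The synopsis calls the expansion cohorts hypothesis-generating, and SAP Section 9.10 performs no tests on study endpoints.

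**Conclusion.** The point holds as a defect of moderate severity in endpoint wording. Section 7.3 lets a non-metastatic skin lesion count as RECIST 1.1 progression, and neither document takes it out again. Any resulting bias lowers apparent efficacy.

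Its size cannot be established. The figure of at most about 1 to 3 subjects per 30 rests entirely on the assumed 3% to 10% rate and on every such lesion being scored as PD. The cost of 3.3 ORR points applies only to a response that the lesion pre-empts, and it is small beside a 95% interval about 31 points wide (38.6 − 7.7 = 30.9). It would be tempting to conclude that the efficacy results are unreliable. The documents do not support that: no case is described, the primary endpoints concern DLTs and adverse events, and the efficacy analyses are descriptive.

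**What to change.** These changes concern endpoint classification only and leave all treatment rules as they are.

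1. In Protocol Section 7.3, replace new cutaneous lesions with new cutaneous lesions judged to be metastases of the study tumour. Histology decides where the biopsy already required for suspicious lesions was done; assessor judgement decides otherwise.
2. In SAP Sections 14.1 to 14.3, state that lesions shown to be keratoacanthoma, hyperkeratosis or primary skin cancer are not RECIST new lesions. Check that the IRC charter says the same.
3. Reconcile the PD definitions for PFS and duration of response between Protocol 8.5.3.1 and SAP 14.2 and 14.3.
4. List every PD that rests only on a skin lesion, and repeat ORR, duration of response and PFS without the PDs not judged metastatic. SAP Section 6.1 says that the report and its addendum are complete and that no final analysis will follow, so this would be run on the data behind those reports. The planned listings already hold the site of new lesions and the start dates of skin adverse events.

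Biopsy should not be the only route to PD. It is required for suspicious lesions, not for every new lesion, and a true skin metastasis left unbiopsied would then be missed, which would bias efficacy upward.

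The cost is a sentence or two in each document, one listing and one sensitivity analysis, with no new procedure. The downside is some assessor judgement for lesions that were not biopsied.
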